7.3.2 Device Deficiency/Malfunction Reporting

Sites should report all device deficiencies/malfunctions on the appropriate CRF form.

The investigator must report all device deficiencies/malfunctions to the Sponsor as soon as possible but no later than outlined below.

Clinical Sites	Reporting timelines
All Sites	Sites must report device deficiencies/malfunctions to the Sponsor no later than 3 calendar days from the day the site personnel became aware of the event or as per the investigative site's local requirements, if the requirement is more stringent than those outlined.

Sites must report device deficiencies/malfunctions to the IRB/EC per the investigative site's local requirements.

Sites should return the device to the Sponsor, if possible.

Sites will have access to an offline form to allow the investigator to report device deficiencies/malfunctions if sites cannot enter the information in the EDC system. This does not replace the EDC reporting system. Sites must still enter all information in the EDC system as soon as feasible.

In case a device deficiency/malfunction occurred before the patient ID has been assigned, sites should report the device deficiency to the Sponsor via the offline reporting form. This does not replace the EDC reporting system. Sites must still enter all information in the EDC system as soon as feasible.

7.3.3 Adverse Event Reporting to Country Regulatory Authorities by the Sponsor

The Sponsor will report SAEs and reportable device deficiencies/malfunctions to the country regulatory authority, per local requirements.

Note: Reportable device deficiencies/malfunctions include device deficiencies/malfunctions that might have led to an SAE if a) suitable action had not been taken or b) intervention had not been made or c) if circumstances had been less fortunate. These are handled under the SAE reporting system.

8 STATISTICAL CONSIDERATIONS

8.1 Analysis Populations

All registered subjects will be included in the analysis.

8.2 Statistical Analyses

The JETi Hong Kong PMS has not been powered to evaluate a hypothesis. Categorical variables will be summarized using frequency counts and percentages. Continuous variables will be summarized using means, standard deviation, median, min and max. Ninety-five percent confidence interval may be computed for exploratory purposes.

8.2.1 Primary Endpoints Analyses

The primary endpoints are:

Arterial and Arteriovenous subjects

For subjects treated for lower extremity arterial thrombosis, the primary endpoints are:

- **Clot removal grade** for each JETi-treated target vessel from pre-JETi angiogram to post-JETi angiogram (post-JETi thrombectomy and prior to any adjunctive therapies to treat underlying culprit lesions) per the grades in **Table 1** (vessel basis). The independent imaging core laboratory will be responsible for assessing this endpoint.
- **Composite of JETi-related major adverse events** (MAEs), defined as the following JETi-related events: device-related death, major amputation of the treated limb (arterial subjects only), or major bleeding up to 30 days post registration and as adjudicated by a clinical events committee (CEC) (subject basis). Refer to Appendix II for definitions of major adverse events.

Table 7. Clot Removal Grade

Grade I	< 50% reduction
Grade II	50- <95% reduction
Grade III	95 - 100% reduction

Venous Subjects

For this study, lower extremity deep vein thrombosis or deep venous thrombosis is defined as lower extremity venous thrombosis involving the femoral, common femoral, iliac, popliteal, or inferior vena cava (IVC) alone or in combination.

For subjects treated for lower extremity DVT, the primary endpoints are:

- **Percent of treated vessel(s) with $\geq 75\%$ venous thrombus reduction** from pre-JETi venogram to final venogram (post-JETi AND after any/all adjunctive therapies to treat underlying culprit lesions) via modified Marder score (limb basis). The independent imaging core laboratory will be responsible for assessing this endpoint.

- **Composite of JETi-related major adverse events (MAEs)** up to 30 days post-JETi procedure, defined as the following JETi-related events adjudicated by a clinical events committee (CEC): death, symptomatic pulmonary embolism (PE), major bleeding, or re-thrombosis of JETi-treated vessel(s). Refer to **Appendix II** for definitions of major adverse events.

8.3 Sample Size Calculation

A total of approximately 20 subjects will be registered in this study.

8.4 Timing of Analysis

Analysis will be performed after all registered subjects have reached their 30-day follow-up visit.

8.5 Subgroup Analysis

8.6 Multiplicity

8.7 Pooling Strategy

Analysis will be performed by pooling data [REDACTED]
[REDACTED]

8.8 Procedures for Accounting for Missing Data

Analysis will be based on available data with missing data excluded. Any unused or spurious data will be noted as appropriate in the final report.

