4.1 Primary Endpoints

4.1.1 Arterial and Arteriovenous Subjects

For subjects treated for arterial thrombosis (may include diagnoses such as acute limb ischemia, chronic limb ischemia/chronic limb threatening ischemia, peripheral artery disease, etc.) or arteriovenous (AV graft, AV fistula) thrombosis, all endpoints are descriptive.

For subjects treated for arterial or arteriovenous thrombosis, the primary endpoints are:

- **Clot removal grade** for each JETi-treated target vessel from pre-JETi angiogram to post-JETi angiogram (post-JETi thrombectomy and prior to any adjunctive therapies to treat underlying culprit lesions) per the grades in **Table 1** (vessel basis). The independent imaging core laboratory will be responsible for assessing this endpoint.
- **Composite of JETi-related major adverse events** (MAEs) up to 30 days post-JETi procedure, defined as the following JETi-related events adjudicated by a clinical events committee (CEC) (subject basis) death, major amputation of the treated limb, or major bleeding. Refer to **Appendix II** for definitions of major adverse events.

Table 1. Clot Removal Grade

Grade I	< 50% reduction
Grade II	50- <95% reduction
Grade III	95 - 100% reduction

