5.2 Subject Recruitment/Screening and Informed Consent

5.2.1 Subject Recruitment and Screening

A member of the site's study team previously trained to the CIP should evaluate patients for general study eligibility criteria. A patient who does not satisfy all general eligibility criteria prior to informed consent is considered a recruitment failure and should not be enrolled in the study.

Sites will ask patients meeting general inclusion criteria and no general exclusion criteria to sign an Informed Consent Form (ICF) following the established Informed Consent process (described in **Section 5.2.2**) if they wish to participate in the study.

Enrolled (consented) subjects who do not have a JETi Catheter introduced into the intended vasculature are considered a screen failure and should be withdrawn from the study. The Principal Investigator or the delegated study personnel will record the screen failure in the hospital records and on a recruitment/screening log as required.

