5.5 Subject Registration

An enrolled subject is considered registered in the study only after a JETi Catheter is introduced into the intended vasculature of the subject during the procedure (Day 0). Patients may be consented after the procedure if all assessments needed for the primary endpoints are complete. A subject who is enrolled but not registered in this study will be considered a screen failure. The sample size of the study is based on the number of registered subjects.

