6.1 Arterial and Arteriovenous Subjects

At Baseline, demographic information, medications, clinical assessment, physical exam and a medical history will be collected. Laboratory assessments, up to 14 days prior to the procedure, will be recorded and may include estimated glomerular filtration rate (eGFR), serum creatinine (SCr), blood urea nitrogen (BUN), potassium (K), hemoglobin (Hgb), platelets (plt), prothrombin time (PT), international normalized ratio (INR) and activated partial thromboplastin time (aPTT).

The pre-JETi angiogram will be used to assess the initial degree of clot burden after catheter insertion into the vessel and prior to JETi Thrombectomy. The post-JETi Thrombectomy angiogram will be used to assess clot removal after JETi Thrombectomy and prior to any adjunctive therapies used to treat underlying culprit lesions. The final angiogram will be completed to assess clot removal after JETi Thrombectomy and any/all adjunctive therapies and prior to removal of the vascular sheath. All treated

vessels will be assessed using the provided clot removal grades (**Table 1**). All angiograms are requested to be transmitted to the core lab for analysis. Guidance from the imaging core laboratory will be provided for reference.

DUS will be collected at baseline and 30-Day Follow-Up for subjects with arteriovenous thrombosis. Refer to the DUS core laboratory guidelines for detailed information. All DUS completed are requested to be transmitted to the core lab for analysis.

An ABI examination is required at Baseline and 30 Days. Rutherford classification is required at Baseline and 30 Days. Note: baseline ABI (within 3 months prior to procedure) and Rutherford assessment (within 4 days prior to procedure) can be obtained via a non-study physician, including a referring physician; this will not be considered a protocol deviation. Note these are applicable to lower extremity arterial subjects only.

The Short Form (SF)-12 is a self-reported outcome quality of life measure. Its completion is requested at Baseline and at 30 days. For post-procedurally consented subjects, a baseline SF-12 will not be collected as the validity of this assessment is not supported when collected retrospectively.

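### The available-case rule in Section 8.8 drops registered cases without a gradable image pair from the primary clot-removal result, mainly in arterial/AV subjects, and nothing bounds the effect

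*Combined protocol and SAP*

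**What the plan says.** All references are to the combined protocol and SAP.

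- **Population (8.1):** "All registered subjects will be included in the analysis".
- **Registration (5.5):** a subject "is considered registered in the study only after a JETi Catheter is introduced into the intended vasculature". Treatment need not be completed.
- **Before registration (5.2.1):** "Enrolled (consented) subjects who do not have a JETi Catheter introduced into the intended vasculature are considered a screen failure".
- **Missing data (8.8):** "Analysis will be based on available data with missing data excluded". A second sentence says that unused or spurious data will be noted in the final report as appropriate. Section 8.8 makes no exception for primary endpoints and gives no failure rule or sensitivity analysis.
- **Arterial/AV primary endpoint (4.1.1, repeated in 8.2.1):** a three-level grade "for each JETi-treated target vessel from pre-JETi angiogram to post-JETi angiogram". The second image is taken before adjunctive therapy. Grade I is "< 50% reduction".
- **Lower-extremity DVT primary endpoint (4.1.2):** percent of treated vessels with at least 75% thrombus reduction, from the pre-JETi venogram to the final venogram, which follows all adjuncts. If no adjunct is used, the post-JETi score also serves as the final score.
- **Other venous subjects (4.1.2):** the clot removal grade of 4.1.1.
- **Image submission:** for arterial/AV subjects (6.1), "All angiograms are requested to be transmitted to the core lab for analysis". Section 6.2 says that venograms will be transmitted.

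**The concern.** The study has no hypothesis test (Section 4), so the reported grade distribution and proportions are its main product. A reader will take them as performance in everyone in whom JETi was used, because 8.1 says so. Under 8.8 they describe only vessels with a gradable image pair.

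For the arterial/AV grade, that loss can plausibly depend on outcome. The second image belongs to a narrow moment: after JETi and before any adjunct. If the device is abandoned, or the operator converts at once to another treatment, that moment may pass without an image. The vessel is then ungradable and drops out, although it would probably have been Grade I. No substitution rule covers this. The rules in 4.1.2 and 4.2.2 let a post-JETi score stand in for a final score when no adjunct is used; none replaces a missing post-JETi angiogram. At stake is an understated Grade I share, with nothing in the report to show by how much.

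**Working it through.** **No figure of the plan to reproduce.** The sample size of about 20 (8.3) has no derivation, and no missing-image rate, target rate or precision is stated. The check traces which cases leave the denominator and then sizes the effect under assumed inputs.

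**Step 1: which cases 8.8 removes.**

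| Case | Outcome under the plan |
|---|---|
| Catheter never introduced | Screen failure (5.2.1); 8.8 not involved |
| Introduced, JETi fails, image pair available | Grade I, or below 75%; counted |
| Introduced, arterial/AV or other venous, no gradable post-JETi image | Dropped by 8.8 |
| Introduced, lower-extremity DVT, converted, final venogram taken | Counted, possibly as a success |
| Introduced, lower-extremity DVT, no gradable final venogram and no substitute score | Dropped by 8.8 |

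The third row is the main exposure.

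**Step 2: formula.** Let N be the registered units, m the ungradable units, p_obs the success rate among gradable units and p_miss the unknown rate among ungradable units. The available-case rate minus the all-registered rate is

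bias = (m/N) × (p_obs − p_miss).

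It is positive if the missing cases did worse, zero if they did equally well and negative if they did better.

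**Step 3: illustration.** Assumed: N = 20 units, one vessel per subject, endpoints pooled, success taken as Grade II or III (the plan sets no threshold), 15 successes, 3 imaged failures, m = 2. Intervals are exact (Clopper-Pearson) 95%.

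| Handling of the 2 ungradable units | Success | Grade I share |
|---|---|---|
| Excluded (8.8) | 15/18 = 83.3% (58.6 to 96.4) | 3/18 = 16.7% |
| Both failures | 15/20 = 75.0% (50.9 to 91.3) | 5/20 = 25.0% |
| Both successes | 17/20 = 85.0% (62.1 to 96.8) | 3/20 = 15.0% |

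Formula check: (2/20) × (0.833 − 0) = 8.3 points, about 4.2 per dropped failure. With p_miss = 1, (2/20) × (0.833 − 1) = −1.7 points.

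**Step 4: range.** N = 20, p_obs from 75% to 90%:

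| m | All missing are failures | Missing equal observed | All missing are successes |
|---|---|---|---|
| 1 | +3.8 to +4.5 points | 0 | −0.5 to −1.2 |
| 2 | +7.5 to +9.0 | 0 | −1.0 to −2.5 |
| 3 | +11.2 to +13.5 | 0 | −1.5 to −3.8 |
| 4 | +15.0 to +18.0 | 0 | −2.0 to −5.0 |

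The endpoints are reported by vascular territory, so actual denominators will be smaller than 20. In an assumed stratum of 10 with one ungradable failure, 8/9 = 88.9% compares with 8/10 = 80.0%.

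**The case against.** A reader might infer that device and crossing failures as a class leave the denominator, and that the result is always flattering. The documents do not support either claim. Imaged failures are counted. Failures before introduction are removed by the registration rule. The direction of bias depends on p_miss, and a transmission that is only requested points as much to ordinary logistic loss as to device failure. That images are lost mostly after failure is plausible but assumed. The lower-extremity DVT endpoint is much less exposed, because the final venogram in 6.2.2 is due after adjuncts and would normally exist even after conversion.

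Sections 8.1 and 8.8 can also be read together: one names the population, the other handles missing values within it. A subject with one ungradable vessel still contributes safety data and any other graded vessels. Device deficiencies must be reported within 3 calendar days (7.3.2), so a malfunction would not go unrecorded. At an observed 17/20 = 85.0% the interval runs from 62.1 to 96.8, so one or two exclusions move the estimate by less than its sampling uncertainty. No decision rule depends on it.

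These points stand and limit the concern; they do not remove it. On the compatible reading, the primary result still omits registered vessels without saying how they did. A deficiency report does not put a vessel back in the denominator, and a wide interval does not correct a systematic shift, particularly as intervals are optional (8.2). The note on unused data does not require counts or reasons.

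The public copy shows no text under 8.5 and 8.6, 8.7 is partly redacted, and the core laboratory guidelines are separate (Appendix IX). A rule for ungradable images could be there.

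**Conclusion.** The concern holds in limited form. Section 8.8 removes registered cases without a gradable image pair from the primary clot-removal result, and no readable text scores them as failures or bounds their effect. The arterial/AV grade, and other venous subjects graded the same way, carry most of the exposure. If the missing cases did worse than the observed ones, the Grade I share is understated. With 20 units the shift is about 4 points per dropped failure, on the assumptions that each missing case is a failure and that observed success is 75% to 90%. The number of missing images is unknown.

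Severity is moderate. A must-fix rating would be too strong for a descriptive study of about 20 subjects. The rule should nevertheless be set in advance, because one chosen after seeing so few results would carry little weight.

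**What to change.** 1. **Section 8.8:** for the primary effectiveness endpoints, keep in the denominator every vessel or limb in which JETi was attempted after catheter introduction.
2. **Sections 4.1 and 8.2.1:** align the endpoint wording. The arterial/AV endpoint counts only JETi-treated vessels and the DVT endpoint only treated vessels, so an attempted but untreated vessel could still fall out if 8.8 alone were changed. Define both terms to include attempted vessels.
3. **Scoring:** where the required image is absent because of device failure, failure to cross, abandonment or conversion, score Grade I (arterial/AV and other venous) or below the 75% threshold (lower-extremity DVT). The existing DVT substitution rule stays.
4. **Other missing images:** report the available-case result with worst- and best-case bounds, and tabulate the number missing and the reasons.
5. **Section 8.1:** cross-refer to the new rule so that population and denominator agree.

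This does not address the separate selection in 5.5, under which consent after the procedure is allowed only if the primary-endpoint assessments are complete. That should be stated as a limitation.

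The cost is protocol and SAP wording, one case report form field for the reason an image is missing, and a reported rate that may be less favourable.

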9 DIRECT ACCESS TO SOURCE DATA/DOCUMENTS

The investigator/institution will permit direct access to source data/documents for performing study-related monitoring, audits, IRB/EC review and regulatory inspections.

Subjects providing informed consent agree to allow study monitors or regulatory authorities, including foreign countries, to review in confidence any records identifying the subjects in this study. This information may be shared with regulatory agencies; however, the Sponsor undertakes not to otherwise release the subject's personal and private information.

10 QUALITY CONTROL AND QUALITY ASSURANCE

10.1 Selection of Clinical Sites and Investigators

The Sponsor will select investigators qualified by training and experience to participate in the study. Sites will be selected based upon review of a recent site assessment, if applicable, and the qualifications of the investigators who will participate in the study.

10.2 CIP Amendments

The Sponsor will provide approved CIP amendments to the Investigators prior to implementing the amendment. The Principal Investigator is responsible for notifying the IRB/EC or equivalent committee of the CIP amendment (administrative changes) or obtaining IRB's/EC's approval of the CIP amendment (changes in subject care or safety), according to the instructions provided by the Sponsor with the CIP amendment.

Sites must document in writing acknowledgement/approval of the CIP amendment by the IRB/EC prior to implementation of the CIP amendment. Sites must also provide copies of this documentation to the Sponsor.

10.3 Training

10.3.1 Site Training

All Investigators and study personnel are required to attend Sponsor training sessions, which may be conducted at an Investigator's meeting, a site initiation visit, or other appropriate training sessions. Over-the-phone or self-training may take place as required. Training of Investigators and study personnel will include, but is not limited to, the CIP requirements, device usage, electronic case report form completion, and study personnel responsibilities. All Investigators and study personnel that are trained must sign a training log (or an equivalent) upon completion of the training.

10.4 Monitoring

Sponsor and/or designee will monitor the study over its duration according to the CIP-specific monitoring plan which will include the planned extent of source data verification.

Prior to initiating any procedure, the Sponsor monitor (or delegate) will ensure that the following criteria are met:

- The investigator understands and accepts the obligation to conduct the study according to the CIP and applicable regulations and has signed the Investigator Agreement or the Clinical Trial Agreement.
- The Investigator and his/her staff should have sufficient time and facilities to conduct the study and should have access to an adequate number of appropriate subjects to conduct the study.
- Sites must have source documentation (including original medical records) to substantiate proper informed consent procedures, adherence to CIP procedures, adequate reporting and follow-up of adverse events, accuracy of data collected on case report forms, and device information.
- The Investigator/site will permit access to such records and will maintain a monitoring visit sign-in log at the site. The Investigator will agree to dedicate an adequate amount of time to the monitoring process. The Investigator and/or research coordinator will be available for monitoring visits. It is expected that the Investigator will provide the monitor with a suitable working environment for review of study-related documents.

10.5 Deviations from CIP

The Investigator should not deviate from the CIP for any reason except in cases of medical emergencies when the deviation is necessary to protect the rights, safety, and well-being of the subject, or to eliminate an apparent immediate hazard to the subject. In that event, the Investigator will notify Sponsor immediately by phone or in writing.

All deviations will be collected, with the following exception:

- Baseline SF-12 in post-procedure consented subjects

The following deviations will be considered major:

- Late SAE, SADE, DD reporting
- Lack of patient informed consent
- Inclusion/exclusion criteria violations.

The Sponsor will not grant any waivers for CIP deviations. Sites must report all deviations to the Sponsor using the Deviation CRF. The Sponsor will monitor the occurrence of CIP for evaluation of investigator compliance to the CIP and regulatory requirements and handle according to written procedures. Investigators will inform their IRB/EC or equivalent committee of all CIP deviations in accordance with their specific IRB/EC or equivalent committee reporting policies and procedures.

In the event of repeated non-compliance, as determined by the Sponsor, a Sponsor's monitor or company representative will attempt to secure compliance by one or more of the following (and not limited to):

- Visiting the investigator and/or delegate
- Telephoning the investigator and/or delegate

- Corresponding with the investigator and/or delegate

Repeated non-compliance with the signed agreement, the CIP, or any other conditions of the study may result in further escalation in accordance with the Sponsor's written procedures, including securing compliance or, at its sole discretion, the Sponsor may terminate the investigator's participation in the study.

